1.2 Schedule of Assessments (SoA)

Table 2. Schedule of Assessments (SoA)

Study day relative to 1 st vaccination	-28 to -1	1	2	4	8	15	29											
Study day relative to 2 nd vaccination							1	2	4	8	15	29	57	180	ET ¹	U ²		
Visit window in days			+1	+1	+1	+/- 1	+3	+1	+1	+1	+/- 1	+/- 4	+/- 4	+/- 7				
Study visit	00 ³	01	01a	02	02a	03	04	04a	05	05a	06	07	08	09				
Visit type ⁴	I	I	P	I	P	I	I	P	I	P	I	I	I	I	I	I		
Obtain informed consent ⁵	X																	
Assessment of eligibility ⁶	X	X					X											
Review of medical history	X	X					X											
Concomitant meds	X ⁷	X	X	X	X	X	X	X	X	X	X	X	X	X	X ⁸	X ⁸		
Vital signs ⁹	X	X		X		X	X		X		X	X	X ¹⁰	X ¹⁰	X ^{8,10}	X ¹⁰		
Perform physical exam ¹¹	X																	
Height and weight ¹²	X																	
Counseling ¹³	X	X		X		X	X		X		X				X ⁸			
Review of contraceptive/menstrual history ¹⁴	X	X					X											
Pregnancy test ^{15, 16}	X	X					X											
HIV antibody ELISA, anti-HCV antibody, HBsAg	X																	
Blood for clinical screening labs ¹⁷	X																	
Urine for screening lab ¹⁸	X																	
Targeted physical exam ¹⁹		X ¹⁹		X ¹⁹		X ¹⁹	X ¹⁹		X ¹⁹		X ¹⁹	X ¹⁹	X ¹⁹	X ¹⁹	X ¹⁹	X ¹⁹		
Randomization ²⁰		X																
Vaccination ²¹		X					X											

Study day relative to 1 st vaccination	-28 to -1	1	2	4	8	15	29								ET ¹	U ²		
Study day relative to 2 nd vaccination							1	2	4	8	15	29	57	180				
Visit window in days			+1	+1	+1	+/- 1	+3	+1	+1	+1	+/- 1	+/- 4	+/- 4	+/- 7				
Study visit	00 ³	01	01a	02	02a	03	04	04a	05	05a	06	07	08	09				
Visit type ⁴	I	I	P	I	P	I	I	P	I	P	I	I	I	I	I	I		
Evaluate vaccination site				X		X			X		X				X ⁸	X ⁸		
Blood for clinical safety labs ¹⁶ ¹⁷		X		X		X	X		X		X				X ²²	X ²²		
Urine for safety lab ²³		X				X	X				X				X ²²	X ²²		
Blood for YFV neutralizing assays ¹⁶		X				X	X				X	X	X	X ²⁶	X ²²	X ²²		
Blood for viremia testing				X					X						X ²²	X ²²		
Identification of unsolicited adverse events ²⁴		X	X	X	X	X	X	X	X	X	X	X			X ⁸	X ⁸		
Identification of medically-attended adverse events ²⁴		X	X	X	X	X	X	X	X	X	X	X	X	X	X	X		
Identification of serious adverse events ²⁴		X	X	X	X	X	X	X	X	X	X	X	X	X	X	X		
Identification of new onset of chronic condition ²⁴		X	X	X	X	X	X	X	X	X	X	X	X	X	X	X		
Review memory aid data			X	X	X			X	X	X					X ²⁵	X ²⁵		

¹ET=early termination visit.

²U=unscheduled visit.

³Screening procedures are performed at visit 00.

⁴Visit type: I=In-person, P= Phone.

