8.5 Adverse Events and Serious Adverse Events

8.5.1 Definition of Adverse Events (AE)

Adverse event means any untoward medical occurrence associated with the use of an intervention in humans, whether or not considered intervention-related (21 CFR 312.32 (a)). An AE can therefore be any unfavorable and unintended sign (including an abnormal laboratory finding), symptom, or disease temporally associated with the use of medicinal (investigational) product.

Any medical condition that is present at the time that the subject is screened will be considered as baseline and not reported as an AE. However, if the severity of any pre-existing medical condition increases, it should be recorded as an AE.

Adverse events can be further divided into solicited adverse events and unsolicited adverse events. Solicited adverse events are those for which the study team will specifically query the participant whether they occurred. Unsolicited adverse events are those events that the subject report occurring without being queried about the specific event.

All AEs will be assessed for severity and relationship to study intervention (see Section [8.5.3.2](#)).

All AEs, solicited and unsolicited, will be captured on the appropriate data collection form. Information to be collected for AEs includes event description, date of onset, assessment of severity, relationship to study product and alternate etiology (assessed only by those with the training and authority to make a diagnosis and listed on the FDA Form 1572 as an investigator), date of resolution, seriousness and outcome. AEs occurring during the trial collection and reporting period will be documented appropriately regardless of relationship. In addition, all medically-attended adverse events (MAAEs) (i.e., events for which medical care from a healthcare provider is sought) will be collected through Study Visit 09.

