8.5.4 Time Period and Frequency for Event Assessment and Follow-up

For this study all solicited AEs will be documented for the 8 days following study product administration.

For this study, all unsolicited, non-serious AEs will be documented from Study Visit 01 (Day 1) through Study Visit 07 (Day 29 post second vaccination).

All MAAEs, SAEs and new onset chronic medical conditions (NOCMC) will be documented from Study Visit 01 (Day 1) through Study Visit 09 (final visit).

Resolution of an AE is defined as the return to pre-treatment status or as stabilization of the condition, with the expectation that it will remain chronic. Site PIs are required to follow all reported AEs until either resolution of the AE or until the event is stable, as determined by the site PI; all SAEs will be followed until either resolution

of the SAE or until the SAE is stable, as determined by the PI. Subjects who have an unresolved SAE at either the final study visit or at discontinuation of study participation will continue to be followed, with the subject's permission, until the SAE is stable/deemed chronic, as determined by the site PI.

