8.5.7 Adverse Events of Special Interest

This study will also assess New-Onset Chronic Medical Conditions (NOCMCs) from the day of receipt of the first dose of study product until study completion. NOCMCs are defined as any new ICD-10 diagnosis (10th revision of the International Statistical Classification of Diseases and Related Health Problems) that is applied to the subject during the course of the study, after receipt of the study agent, that is expected to continue for at least 3 months and requires continued health care intervention. NOCMCs will be assessed and recorded as unsolicited AEs.

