3.2. Endpoints

Primary Outcome Measures:

- Occurrence of all serious adverse events (SAEs) at any time during the study
- Occurrence of all Grade 3 unsolicited adverse events (AEs) from first vaccination through Day 29 after the second vaccination
- Occurrence of all Grade 3 laboratory toxicities from first vaccination through Day 15 after the second vaccination
- Occurrence of solicited local AE and reactogenicity signs and symptoms in the 7 days after each vaccination
- Occurrence of solicited systemic AE and reactogenicity signs and symptoms in the 7 days after each vaccination
- Occurrence of any AE through Day 29 after the second vaccination

Secondary Outcome Measures:

- Percentage of subjects achieving seroconversion ($\geq 1:10$ in plaque reduction neutralizing titer [PRNT₅₀] titer, at Day 29 after first vaccination and at Day 29 after second vaccination
- Geometric mean neutralizing titers at days 15 and 29 after first vaccination and at Days 15, 29, and 57 following second vaccination
- Reverse cumulative distribution curve of neutralizing titers on Days 15 and 29 after first vaccination and at Days 15, 29 and 57 after the second vaccination for each dose group and for all dose groups combined

Exploratory Outcome Measures:

- Geometric mean neutralizing titers at Day 180 following second vaccination
- Reverse cumulative distribution curve of neutralizing titers on Day 180 after the second vaccination for each dose group and for all dose groups combined

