8.1. Adverse Events

When calculating the incidence of adverse events (i.e., on a per subject basis), each subject will only be counted once and any repetitions of adverse events within a subject will be ignored; the denominator will be the total population size. All adverse events reported will be included in the summaries and analyses.

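### Two primary AE endpoints end at Day 29 after dose 2, but SAP 8.1 and the AE table shells do not apply that limit, and no table shell reports any AE

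*SAP*

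**What the plan says.** **Endpoints.** SAP 3.2 lists among the primary outcomes "Occurrence of all Grade 3 unsolicited adverse events (AEs) from first vaccination through Day 29 after the second vaccination" and "Occurrence of any AE through Day 29 after the second vaccination". Serious AEs, by contrast, count over the whole study. Protocol sections 3 and 9.4.2 give the same windows.

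**Analysis rule.** SAP 8.1 counts each subject once, uses the total population as denominator, and adds: "All adverse events reported will be included in the summaries and analyses". SAP 8.1.1 describes Table 9 as covering all recorded AEs. The titles, rows and footnotes of Tables 9 and 23 state no time window.

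**Collection.** Under protocol 8.5.4, unsolicited non-serious AEs are documented up to Visit 07, which is Day 29 after dose 2. The same section continues: "All MAAEs, SAEs and new onset chronic medical conditions (NOCMC) will be documented from Study Visit 01 (Day 1) through Study Visit 09". Protocol 8.5.7 adds: "NOCMCs will be assessed and recorded as unsolicited AEs".

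**Shells.** Table 9 has separate rows for local solicited, systemic solicited, unsolicited, laboratory and serious events. Its footnote allows a subject to appear in several of them. Table 10 covers solicited events only and Tables 23-24 unsolicited events only. Tables 25-27 show unsolicited AEs by period, and the last period runs from Day 16 to Day 57 after dose 2.

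**The concern.** Safety is the primary objective, and the endpoint windows are part of what is being estimated. A programmer who follows SAP 8.1 and the shells literally could place an event with onset after Day 29 in the Grade 3 unsolicited row, which would then cover a longer period than its endpoint. The any-AE endpoint has a different problem: it has a definition and a counting rule, but no table row in which to report it.

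Neither point can be checked from listings at the Day 57 analysis, because SAP 6.3 defers all subject listings to the end of the study. At the end, a late Grade 3 event could be picked out by hand, since Listings 3 and 4 show days since the associated dose. The any-AE rate could not be rebuilt from those two shells, because they omit mild non-serious AEs. It would depend on the general intention in SAP 6.1 and protocol 9.4.6 to list all data.

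**Working it through.** **1. Which events can fall outside the window.** The limits by event type, from SAP 3.2 and protocol 8.5.4 and 8.5.7:

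- Ordinary unsolicited non-serious AEs: collected to Visit 07. Collection itself supplies the cut-off, give or take the visit window.
- New-onset chronic medical conditions (NOCMCs): collected to Visit 09 and expressly recorded as unsolicited AEs. These can enter the unsolicited rows late.
- Medically attended AEs (MAAEs) and SAEs: collected to Visit 09. The documents do not say outright that they enter the unsolicited rows; this is an inference.

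So the gap is real but narrow. Because any AE has no row, the existing primary result exposed is Grade 3 unsolicited AEs, in Tables 9 and 23.

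**2. Size of one late event.** Inputs: 10 vaccine recipients per dose group and 5 placebo recipients (protocol 9.2). Method: two-sided exact (Clopper-Pearson) 95% interval.

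- The plan's own figure, 0/10: upper bound = 1 - 0.025^(1/10) = 0.308. This reproduces the 30.8% in protocol 9.2.1 and SAP 5.
- 1/10: lower bound = 1 - 0.975^(1/10) = 0.0025. The upper bound solves (1-p)^10 + 10p(1-p)^9 = 0.025, giving p = 0.445. The interval is 0.3 to 44.5%.
- 0/5: upper bound = 1 - 0.025^(1/5) = 0.522. The interval is 0 to 52.2%.
- 1/5: lower bound = 1 - 0.975^(1/5) = 0.0051; upper bound 0.716. The interval is 0.5 to 71.6%.

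One subject whose only Grade 3 unsolicited event is late therefore moves the observed rate by 10 points in a dose group and 20 points in placebo. A subject who already has an in-window Grade 3 event moves nothing.

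**3. Why existing rows do not give any AE.** Let a be the subjects with any solicited symptom (Table 10) and b those with any unsolicited AE (Table 23). Any AE then lies between max(a, b) and min(10, a + b). With counts chosen only for illustration, a = 6 and b = 3, it lies between 6/10 (exact 95% CI 26.2 to 87.8%) and 9/10 (55.5 to 99.7%). The overlap is not shown anywhere in the shells.

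**4. The last column of Tables 25-27.**

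- Length: 57 - 16 + 1 = 42 days.
- Full collection, Days 16-29: 29 - 16 + 1 = 14 days.
- MAAE, SAE and NOCMC collection only, Days 30-57: 57 - 30 + 1 = 28 days, and 28/42 = 67%.
- Visit 07 may fall 4 days either side (protocol Table 2). At Day 25 the partial share is 32/42 = 76%; at Day 33 it is 24/42 = 57%.
- Dose 2 is on study Day 29, which is Day 1 after dose 2. Day 29 after dose 2 is therefore study Day 29 + 28 = 57. The column label may be a slip between the two day scales.

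**The case against.** The best reply is that the cut-off is already prespecified. SAP 3.2 and protocol 9.4.2 both end these endpoints at Day 29, and a specific endpoint definition can reasonably govern a general sentence about counting. Table 9 states no window for any row, including the laboratory and SAE rows, so it may simply leave all windows to SAP 3.2. This stands in part: the endpoints are defined. What remains is an inclusion rule in the same document that says something broader, with nothing in the shells to settle which applies.

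Second, late entries should be few. An NOCMC must be a new diagnosis expected to last at least 3 months and to need continued care, and it must also be Grade 3 to touch the exposed row. SAEs are a study-wide primary endpoint in their own right. This stands, and it limits the practical effect.

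Third, SAP 8.1.2 promises figures of AE incidence (Figures 6-9), which might show any AE. They sit under the unsolicited heading and their images are not available, so they can be counted neither for the plan nor against it. The finding is limited to table shells.

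Fourth, the Day 57 limit of the last column may be deliberate, to match the primary database. That is possible, but the column would still mix two levels of collection without saying so.

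Finally, the analyses are descriptive, with no formal testing (SAP 6.7), and the Day 57 results do not steer the trial. This keeps the point modest.

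**Conclusion.** The point holds as a reporting gap of limited size, between minor and a change that should be made. SAP 8.1, taken literally, lets late events into the Grade 3 unsolicited rows; no table shell reports the primary any-AE endpoint; and one descriptive column crosses a change in collection. The any-AE gap stands even if no late event ever occurs.

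The size for the Grade 3 row is a per-subject worst case: 0/10 to 1/10 in a dose group. It assumes that a subject's only Grade 3 unsolicited event is late and is programmed into the row. The documents give no rate for such subjects, so no probability is attached.

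A reader might infer three stronger things, and the documents do not support them. The first is that these endpoints have no cut-off at all; SAP 3.2 supplies one. The second is that primary AE rates will be materially inflated; most non-serious AEs are not collected after Visit 07. The third is that the same row is bound to differ between the Day 57 analysis and the clinical study report. It could, but protocol 9.4.4.2 puts the primary database at approximately Day 57 and sets no explicit per-subject cut, so it cannot be said for certain which late events would appear in which analysis.

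Sample size and the design figures are unaffected.

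**What to change.** 1. In SAP 8.1 and the footnotes of Tables 9, 23 and 24, limit unsolicited AE rows to the SAP 3.2 window, meaning onset through Day 29 after dose 2. Keep the SAE rows study-wide. Show later MAAEs, SAEs and NOCMCs in a separate display.
2. Add one row to Table 9 for subjects with at least one AE through Day 29 after dose 2, each counted once, with an exact 95% interval. The shell now carries only counts and percentages, so the interval needs a place. Add a footnote saying whether graded laboratory abnormalities count. It should agree with protocol 8.5.1, whose AE definition covers "any unfavorable and unintended sign (including an abnormal laboratory finding), symptom, or disease".
3. Relabel the last column of Tables 25-27 as Day 16-29 after dose 2, or split it at Day 29.

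The cost is SAP wording and shell edits, with no new data. The only downside is one small extra display for late events.

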8.1.1. Solicited Events and Symptoms

Systemic solicited adverse events will be collected pre-vaccination, and systemic and local solicited adverse events will be collected 30 minutes post-vaccination and then daily for 7 days after each vaccination and graded on a scale of 0 (absent), 1 (mild), 2 (moderate) and 3 (severe). Systemic solicited symptoms will include feverishness, fatigue, headache, chills, nausea, new muscle pain (exclusive of the injection sites), aggravated muscle pain (increase of existing pain, exclusive of the injection site), new joint pain, and aggravated joint pain (increase of existing pain). Local events include: pain at injection site, tenderness at injection site, induration/swelling and erythema/redness. A summary of all recorded adverse events will be provided ([Table 9](#)). A subject-level summary of solicited events by symptom, severity and treatment group post-first, post-second or post-either dose will be presented ([Table 10](#)).

Analysis will also include the number and proportion of solicited systemic and local events over 7 days after each vaccination, as analyzed within each treatment group and after each vaccine administration ([Table 11](#), [Table 12](#), [Table 13](#), [Table 14](#), [Table 15](#), [Table 16](#), [Table 17](#), [Table 18](#), [Table 19](#), [Table 20](#), [Table 21](#), and [Table 22](#)).

The maximum severity of solicited systemic and local events, organized by treatment group, will be summarized for each day post-vaccination (through day 7) in bar charts ([Figure 2](#), [Figure 3](#), [Figure 4](#) and [Figure 5](#)).

8.1.2. Unsolicited Adverse Events

The total number and proportion of subjects reporting unsolicited adverse event will be summarized by MedDRA system organ class and preferred term by severity and treatment group ([Table 23](#)). A subset analysis of related unsolicited adverse events will also be provided ([Table 24](#)). Unsolicited adverse events will also be summarized by time post-treatment for each treatment group ([Table 25](#), [Table 26](#), and [Table 27](#)).

Graphical representations will be provided for overall incidence of adverse events by MedDRA system organ class segregated by treatment group ([Figure 6](#)) and relationship to treatment ([Figure 7](#)), incidence of adverse events by severity ([Figure 8](#)) and incidence of adverse events by relationship to treatment ([Figure 9](#)).

8.2. Deaths, Serious Adverse Events, and other Significant Adverse Events

A listing of all Serious Adverse Events will be provided ([Listing 3](#)).

A listing of non-serious, unsolicited, moderate or severe adverse events will be provided ([Listing 4](#)).

8.3. Pregnancies

For any subjects in the Safety population who became pregnant during the study, every attempt will be made to follow these subjects to completion of pregnancy to document the outcome, including information regarding any complications with pregnancy and/or delivery. The analysis will include information such as the total pregnancies, number of live births, and number of spontaneous abortions, elective abortions or still births by treatment will be presented ([Listing 5](#), [Listing 6](#), [Listing 7](#), [Listing 8](#), and [Listing 9](#)).

8.4. Clinical Laboratory Evaluations

The following laboratory measurements are collected and will be summarized:

- Hematology tests: White blood cell count, hemoglobin, platelets
- Blood chemistry tests: Sodium, potassium, bicarbonate, calcium, creatinine, glucose (non-fasting), ALT, AST, and total bilirubin.
- Urinalysis

Listings of abnormal laboratory results for hematology ([Listing 10](#)) chemistry ([Listing 11](#)) and urinalysis ([Listing 12](#)) will be provided.

The distribution of laboratory results by severity, study day and treatment group will be presented ([Table 28](#)). Abnormal laboratory results related to study treatment will be provided ([Table 29](#)).

8.5. Vital Signs and Physical Evaluations

Vital sign measurements include systolic blood pressure, diastolic blood pressure and oral temperature. Vital signs will be assessed at Day 1, 4, and 15 after each vaccination and through the end of the study if clinically indicated. A vital sign listing for all subjects will be provided ([Listing 13](#)) and a graphical representation of vital signs by assessment, maximum severity, study and treatment group will be presented ([Figure 10](#)).

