7.1 Halting Criteria and Discontinuation of Study Intervention

7.1.1 Study Halting Criteria

Additional enrollment and study interventions/administration of study products in this trial will be halted for SMC review/recommendation if any of the following are reported:

- Any subject experiences ulceration, abscess, or necrosis at the injection site related to study product administration.
- Any subject presents with laryngospasm, bronchospasm, hypotension or anaphylaxis occurring within 24 hours following product administration that is considered related to study product.
- Two or more subjects experience generalized urticaria (defined as occurring at more than two body parts) within 72 hours after administration of study product that is considered related to study product.
- Any subject experiences an SAE after administration of study product and prior to the subject's last visit that is considered related to study product.
- Two or more subjects who received at least one dose of study vaccine to date, cumulative to all study vaccine administrations, across all treatment arms, experience the same Grade 3 (unsolicited AE or safety laboratory), in the same HLT by MedDRA coding, considered related to study product.

This trial will also be halted for SMC review/recommendation if, within 7 days after administration of either study vaccination, any of the following occurs:

- Three or more subjects who received at least one dose of study vaccine to date, cumulative to all study vaccine administrations, across all treatment arms, experience the same severe (Grade 3) study vaccine-related injection site reaction. Erythema and induration (hardness)/edema (swelling) will also be measured in mm but size will not be used as halting criteria.
- Three or more subjects who received at least one dose of study vaccine to date, cumulative to all study vaccine administrations, across all treatment arms, experience the same severe (Grade 3) study vaccine-related subjective systemic reaction, for which the severity (grade) is corroborated by study personnel.
- Three or more subjects who received at least one dose of study vaccine to date, cumulative to all study vaccine administrations, across all treatment arms, experience the same severe (Grade 3) study vaccine-related quantitative systemic reaction.

Grading scales for solicited injection site and systemic (subjective and quantitative) reactions are included in Section [8.5.1.1](#).

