8. STUDY ASSESSMENTS AND PROCEDURES

8.1 Screening and Immunogenicity Assessments

8.1.1 Screening Procedures

Screening procedures may be done up to 28 days prior to enrollment (Day-28 to Day -1). After informed consent the following assessments are performed to determine eligibility and obtain baseline data:

1. Take a focused medical history, including the following information:
 - History of any chronic medical conditions related to inclusion and exclusion criteria.
 - History of any medication allergies including history of hypersensitivity to any components of the study product.
 - Concomitant medications taken within 60 days prior to signing the ICF will be reviewed with subjects to determine stability of chronic diseases and eligibility.
 - Ask if they are participating in another clinical trial or plan to enroll in another clinical trial during the study period.
2. Women of childbearing potentials should be counseled to either practice abstinence or use at least one primary form of contraception from 30 days prior to receipt of study product until 30 days after receipt of the last dose of study vaccine.
3. Sexually active men should be counseled to use contraception from the date of receipt of the first dose of study vaccine until one month after receipt of the second dose of study vaccine.
4. Women of childbearing potential must have a negative serum HCG pregnancy test at screening and a negative urine HCG pregnancy test prior to each dose of study product.
5. Physical exam (standard exam at screening and targeted exam at enrollment).
6. Height and weight measurement (Calculation of Body Mass Index).
7. Vital signs measurement (including HR, BP, oral temperature).
8. Blood for laboratory evaluations.
 - Serology at screening: HIV, Hepatitis B surface antigen, Hepatitis C antibody.
 - Chemistry at screening: sodium, potassium, bicarbonate, calcium, creatinine, glucose [non-fasting], ALT, AST, and total bilirubin.
 - Hematology at screening: white blood cells (WBCs), hemoglobin, and platelet count.
 - Urine for glucose and protein.

Clinical screening laboratory evaluations will be performed locally by the Duke University Health System Clinical Laboratories. Urine pregnancy tests will be performed by trained research staff. The volume of venous blood to be collected is presented in [Table 3](#).

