Systolic blood pressure	mm Hg	Hypertension	141-150	151-160	> 160
Diastolic blood pressure	mm Hg	Hypertension	91-95	96-100	>100
Heart rate	Beats per minute	Tachycardia	101-115	116-130	> 130
		Bradycardia	35-46	30-34	< 30

Respiratory

Table 16. Respiratory toxicity table

Parameter	Grade 1	Grade 2	Grade 3
Cough	transient- no treatment	persistent cough; treatment responsive	Severe cough (interferes with daily activities)
Bronchospasm, Acute	transient; no treatment; 70% - 80% FEV1	requires treatment; normalizes with bronchodilator; FEV1 60% - 70%	no normalization with bronchodilator; FEV1 < 60%
Dyspnea	Does not interfere with usual and social activities	Interferes with usual and social activities; no treatment	Prevents daily and usual social activity or requires treatment

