Treatment Group	Subject ID	Sex	Age (years)	Planned Study Day	Actual Study Day	Laboratory Parameter (Units)	Result (Severity)	Relationship to Treatment	If Not Related, Alternative Etiology	Action Taken with Study Treatment	Subject Discontinued Due to Result?
XXX	XXX.XXX		XX								

Implementation note: Sort order will be Treatment Group (Low Dose, High Dose, Placebo), Subject ID

Listing 12: Listing of Abnormal Laboratory Results – Urinalysis

Urinalysis											
Treatment Group	Subject ID	Sex	Age (years)	Planned Study Day	Actual Study Day	Laboratory Parameter (Units)	Result (Severity)	Relationship to Treatment	If Not Related, Alternative Etiology	Action Taken with Study Treatment	Subject Discontinued Due to Result?
XXX	XXX.XXX		XX								

Implementation note: Sort order will be Treatment Group (Low Dose, High Dose, Placebo), Subject ID

Listing 13: Vital Signs

Treatment Group	Subject ID	Planned Time Point	Actual Study Day	Time	Temperature (C)	Systolic Blood Pressure (mmHg)	Diastolic Blood Pressure (mmHg)	Pulse (beats/min)	Weight (kg)	Height (cm)
XXX	XXX.XXX									

Implementation note: Sort order will be Treatment Group (Low Dose, High Dose, Placebo), Subject ID

Listing 14: Individual Immunogenicity Antibody Response Data for PRNT₅₀ and LNI Titers

Treatment Group	Subject ID	Visit Number	Study Day	PRNT ₅₀ Titer	LNI Titer
XXX	XXX.XXX				

Implementation note: Sort order will be Treatment Group (Low Dose, High Dose, Placebo), Subject ID

Listing 15: Individual Viremia Data

Treatment Group	Subject ID	Visit Number	Study Day	Result
XXX	XXX.XXX			

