APPENDIX 3. FIGURE MOCK-UPS

Figure 1: CONSORT Flow Diagram All Subjects

[figure not shown]
[figure not shown]
[figure not shown]

[figure not shown]
Figure 2: Maximum Severity of Solicited Systemic Symptoms per Subject by Day Post Treatment - Post-Dose 1

Implementation Note: Treatment group labels in the shell are generic. The actual labels will be used in the production version.

Figure 3: Maximum Severity of Solicited Systemic Symptoms per Subject by Day Post Treatment - Post-Dose 2

[figure not shown]
Implementation Note: Treatment group labels in the shell are generic. The actual labels will be used in the production version.

Figure 4: Maximum Severity of Solicited Local Symptoms per Subject by Day Post Treatment - Post-Dose 1

[figure not shown]

Implementation Note: Treatment group labels in the shell are generic. The actual labels will be used in the production version.

[figure not shown]
Figure 5: Maximum Severity of Solicited Local Symptoms per Subject by Day Post Treatment - Post-Dose 2

Implementation Note: Treatment group labels in the shell are generic. The actual labels will be used in the production version.

[figure not shown]
Figure 6: Incidence of Adverse Events by MedDRA® System Organ Class and Severity

Implementation Note: Treatment group labels in the shell are generic. The actual labels will be used in the production version.

Figure 7: Incidence of Adverse Events by MedDRA® System Organ Class and Relationship to Treatment

Implementation Note: Treatment group labels in the shell are generic. The actual labels will be used in the production version.

Figure 8: Incidence of Adverse Events by Severity

[figure not shown]
Implementation Note: Treatment group labels in the shell are generic. The actual labels will be used in the production version.

Statistical Analysis Plan

RESTRICTED

[figure not shown]
Page 105 of 115

Figure 9: Incidence of Adverse Events by Relationship to Treatment

Implementation Note: Treatment group labels in the shell are generic. The actual labels will be used in the production version.

Figure 10: Vital Signs by Assessment, Maximum Severity, Study Day, and Treatment Group

Implementation Note: Assessments will either be displayed in individual panels of a single figure or in separate figures. Treatment group labels in the shell are generic. The actual labels will be used in the production version.

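### SAP 8.5 leaves out pulse and the required Visit 07 vital signs, and the only planned by-arm summary, graded by severity, cannot register low blood pressure

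*SAP*

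**What the plan says.** SAP 8.5 defines the parameters: "Vital sign measurements include systolic blood pressure, diastolic blood pressure and oral temperature". It then gives the timing: "Vital signs will be assessed at Day 1, 4, and 15 after each vaccination and through the end of the study if clinically indicated". It names two outputs. One is a listing ("A vital sign listing for all subjects will be provided", Listing 13). The other is a figure, whose shell is titled "Figure 10: Vital Signs by Assessment, Maximum Severity, Study Day, and Treatment Group". None of Tables 1 to 33 is a vital-sign table.

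The protocol is wider on both counts. Footnote 9 of the Schedule of Assessments (Table 2) counts oral temperature, blood pressure and pulse as vital signs, and Section 8.1.1 includes heart rate at screening. The vital-signs row has a plain X at Visits 00 to 07, apart from the phone contacts. Footnote 10, which makes the measurement conditional on clinical need, is attached only to Visits 08 and 09 and to the early-termination and unscheduled visits. Appendix A, Table 15 grades heart rate for both tachycardia and bradycardia, but systolic and diastolic pressure for hypertension only.

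The SAP is also inconsistent with itself, because the shell for Listing 13 has a pulse column.

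**The concern.** A programmer who follows SAP 8.5 literally would build the vital-sign output without pulse, the only cardiovascular parameter that the protocol grades both high and low. The same programmer would treat Visit 07 as optional. That visit closes the window for the primary outcome of any AE through Day 29 after the second vaccination.

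A second limitation would remain even if pulse were added. Figure 10 plots severity grades, and low blood pressure has no grade, so a fall in pressure looks the same as a normal reading.

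At stake is whether readers of this first-in-human trial can compare pulse and low blood pressure between vaccine and placebo in a summary. The Day 57 analysis feeds a manuscript and may inform later trials (SAP 2.1).

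**Working it through.** The plan states no figure on this point, so the check sets the texts side by side.

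**1. Parameters.** Protocol: systolic pressure, diastolic pressure, pulse, oral temperature = 4. SAP 8.5: systolic pressure, diastolic pressure, oral temperature = 3. Missing: pulse, 1 of 4.

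**2. Visits.** Day 1, 4 and 15 after each dose correspond to Visits 01, 02, 03 (dose 1) and 04, 05, 06 (dose 2).

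| Visit | Protocol schedule | SAP 8.5 |
|---|---|---|
| 01 to 06 | required | named |
| 07 (Day 29 after dose 2) | required | conditional |
| 08, 09 | conditional | conditional |

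There are 7 required visits from Day 1 onward (6 after Day 1) and SAP 8.5 names 6, so 1 of 7 is left out. With 25 subjects, planned readings per parameter are 25 × 6 = 150 under SAP 8.5 and 25 × 7 = 175 under the protocol, a difference of 25.

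**3. What a severity figure can show.** SAP 8 refers to the protocol for grading scales. Applying Table 15 to example values:

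| Parameter | Values | Grade |
|---|---|---|
| Systolic pressure, low | 84, 70, 60 mm Hg | none, none, none |
| Systolic pressure, high | 145, 165 mm Hg | 1, 3 |
| Diastolic pressure, low | 54, 40, 30 mm Hg | none, none, none |
| Diastolic pressure, high | 93, 105 mm Hg | 1, 3 |
| Heart rate, low | 40, 32, 28 per minute | 1, 2, 3 |
| Heart rate, high | 110, 120, 140 per minute | 1, 2, 3 |

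Two of the three cardiovascular parameters are graded upward only. The low pressures lie below the protocol's own entry limits (85 systolic, 55 diastolic), yet none registers. Pulse would register in both directions if it were plotted, although changes inside the ungraded range of 47 to 100 would not.

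**4. Where each reading can appear.**

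| Output | Pulse | Low blood pressure | At the Day 57 analysis |
|---|---|---|---|
| Figure 10 | not stated | cannot register | not withheld |
| Listing 13 | yes, with treatment group | yes, with treatment group | not produced (SAP 6.3) |
| Tables 23 and 24 | if recorded as an AE | if recorded as an AE | not withheld |
| SAP 6.1 general rule | in principle | in principle | no vital-sign shell applies it |

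**The case against.** The case against rests on five points, and most of each stands.

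- **Listing 13 carries the data.** It shows every pulse and pressure with treatment group. With 10, 10 and 5 subjects it can be read by eye. A reader might infer that heart rate and low pressure cannot be shown by arm at all. The documents do not support that: what is missing is a summary, and the listing is missing only at the Day 57 analysis.
- **Events reach by-arm tables.** Tachycardia and bradycardia sit in Table 15 as clinical AEs. Reported hypotension can be graded on the general scale in protocol 8.5.3.1. Both would then appear in Table 23, and in Table 24 if related. This stands, but those tables hold only what was recorded as an event, not the measured values.
- **SAP 6.1 already promises descriptive statistics for all continuous variables.** True, and 8.5 is not a closed list, since Listing 13 reports pulse anyway. The fair criticism is that no shell applies the rule to vital signs.
- **Nothing is expressly excluded.** The Figure 10 shell text does not enumerate its assessments, SAP 4.1 defers to the protocol for the full schedule, and SAP 6.1 says all recorded data are listed. So one cannot say that pulse is barred from Figure 10 or that Visit 07 data will be discarded, only that SAP 8.5 as written requires neither.
- **The halting rule is separate.** Protocol 7.1.1 names "laryngospasm, bronchospasm, hypotension or anaphylaxis occurring within 24 hours following product administration" if considered related to study product. A reader might infer that the output gap weakens this rule. It does not: halting works through event reports and committee review, and after the dosing day the next scheduled vital signs are on Day 4, outside the 24-hour window.

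It is also fair that vital signs are not a named endpoint.

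**Conclusion.** The point holds as a small reporting defect. SAP 8.5 contradicts the protocol and the SAP's own listing shell on pulse (1 of 4 parameters), and contradicts the schedule on Visit 07 (1 of 7 required visits from Day 1). Separately, the one planned by-arm summary of vital signs cannot show low blood pressure, whichever parameters it includes. The practical effect is greatest at the Day 57 analysis, where only Figure 10 and the AE tables could carry this information.

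This rests on two assumptions: that Figure 10 takes its blood-pressure and heart-rate grades from Table 15, and that its mock-up, which is not visible in the text reviewed, does not add measured values. No endpoint, sample-size figure, grading rule or halting rule is called into question.

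**What to change.** 1. Reword SAP 8.5 to systolic and diastolic blood pressure, pulse and oral temperature, required at Visits 01 to 07 and conditional on clinical need only at Visits 08 and 09. Early-termination and unscheduled visits should follow the schedule's footnotes.
2. State in SAP 8.5 and the Figure 10 shell that pulse is included.
3. Add one table shell applying the SAP 6.1 statistics (n, mean, standard deviation, median, minimum, maximum) to vital-sign values and change from the Day 1 baseline value, by arm and visit. Mark it for the Day 57 analysis. Say which Day 1 reading is the baseline: the schedule's footnote requiring completion before vaccination is not attached to the vital-signs row.

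The cost is a few lines of SAP text and one extra descriptive table. The protocol already requires the data. The table shows low pressures as values, so no new grade is needed.
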